4.2 Exclusion criteria

Population fulfilling any of the following criteria are not eligible for inclusion in this study:

1. Asthma exacerbation, within 6 weeks prior to enrolment (screening) that required SCS, hospitalization, or emergency room visit. Patients who experience an exacerbation between screening to end of run-in, prior randomization, to be considered failures and can be eligible for re-screening only once, 6 weeks after recovering from the exacerbation.
2. Chronic/ maintenance use of OCS for asthma (total OCS use days greater than 6 months; continuously or intermittently) within the last year
3. Prior use of biologics (including but not limited to Omalizumab, Mepolizumab, Reslizumab, Dupilumab, Benralizumab etc., for asthma or any other indications) that has potential to interfere/ affect asthma disease progression, in the previous 6 months from run-in period.
4. Any contra-indications of SCS use e.g. diabetes, narrow angle glaucoma, or any other as defined by the treating physician
5. Pregnant or nursing (lactating) women
6. Women of child-bearing potential, defined as all women physiologically capable of becoming pregnant, unless they are using basic methods of contraception during dosing of investigational drug. Basic contraception methods include:

- Total abstinence (when this is in line with the preferred and usual lifestyle of the subject. Periodic abstinence (e.g., calendar, ovulation, symptothermal, post-ovulation methods) and withdrawal are not acceptable methods of contraception)
- Female sterilization (have had surgical bilateral oophorectomy with or without hysterectomy), total hysterectomy or tubal ligation at least six weeks before taking investigational drug. In case of oophorectomy alone, only when the reproductive status of the woman has been confirmed by follow up hormone level assessment
- Male sterilization (at least 6 months prior to screening). For female subjects on the study, the vasectomized male partner should be the sole partner for that subject
- Barrier methods of contraception: Condom or Occlusive cap (diaphragm or cervical/vault caps). For United Kingdom: with spermicidal foam/gel/film/cream/vaginal suppository

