5.6 Study completion and discontinuation

5.6.1 Study completion and post-study treatment

A patient will be considered to have completed the study when the patient has completed the last visit planned in the protocol.

Study completion for a patient will occur after he/she has completed 52 weeks of treatment (through the follow-up visit) or they have prematurely withdrawn. Completion of the study will be when all randomized patients have completed 52 weeks of treatment and the post-treatment follow-up visit.

Patients who have been screened when enrolment target has been met will be allowed to proceed onto study participation.

At the time of study completion or early termination, all patients will be placed on the appropriate asthma treatments as per the investigator judgement.

For all patients a safety follow-up visit should be conducted (e.g. by telephone) 14 days after last dose of study drug. The information to be collected at this follow up visit includes adverse events, and SAEs.

When the patient has completed all scheduled study assessments or prematurely withdrawn from the study, the investigator must contact the IRT to record the patient completion /discontinuation and complete applicable eCRF.

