5.6.2 Discontinuation of study treatment

Discontinuation of study treatment for a subject occurs when study treatment is stopped earlier than the protocol planned duration, and can be initiated by either the subject or the investigator.

The investigator must discontinue study treatment for a given subject if, he/she believes that continuation would negatively impact the subject's well-being.

Study treatment must be discontinued under the following circumstances:

- Withdrawal of informed consent (and the investigator must prematurely withdraw the patient from the study);
- Pregnancy;
- Female subjects non-compliant with the chosen effective method of contraception during the study: The investigator must provide appropriate advice on the continued use of effective contraception for at least one week (at least 5 half-lives of QAW039) after study drug discontinuation and follow up with the subject as appropriate at least to the end of this period;
- Any protocol deviation that results in a significant risk to the patient's safety;
- Liver laboratory test abnormality / event (see [Section 14](#)):
 - Abnormal liver laboratory results requiring discontinuation – refer to [Table 14-2 - Appendix 2](#);
- If the investigator considers it appropriate after the confirmation of a liver safety monitoring signal:

- ALT or AST $\geq 2.5 \times$ ULN **and** total bilirubin $\geq 1.5 \times$ ULN ([Section 14](#));
- Any laboratory abnormalities that in the judgment of the investigator, taking into consideration the subject's overall status, prevents the subject from continuing participation in the study;
- Premature unblinding of study treatment for a patient for any reason; please refer to [Section 5.5.9](#);
- Total white blood cell count < 1000 cells/ μ L;
- If patients on statin therapy complain of persistent muscle pain without any obvious cause for greater than 3 days accompanied by increase in CK levels $> 10 \times$ ULN or persistent intolerable muscle pain regardless of the accompanying CK level;
- If a patient develops a medical condition that requires consistent use of prohibited treatment as per [Section 5.5.8](#) or if patient exhibits a behavior of non-compliance regarding prohibited medication.

If discontinuation of study treatment occurs, the investigator should make a reasonable effort to understand the primary reason for the subject's premature discontinuation of study treatment and record this information.

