5.6.5 Early study termination by the sponsor

The study can be terminated by Novartis at any time for any reason. This may include reasons related to the benefit/ risk assessment of participating in the study, practical reasons (including slow enrollment), or for regulatory or medical reasons. In taking the decision to terminate, Novartis will always consider the subject welfare and safety. Should early termination be necessary, subjects must be seen as soon as possible (provide instruction for contacting the subject, when the subject should stop taking drug, when the subject should come for a final visit) and treated as a prematurely withdrawn subject. The investigator may be informed of additional procedures to be followed in order to ensure that adequate consideration is given to the protection of the subject's interests. The investigator or sponsor depending on the local regulation will be responsible for informing IRBs/IECs of the early termination of the trial.

6 Visit schedule and assessments

Visits must be scheduled to allow randomized study drug to be taken in the morning.

[figure not shown]

Table 6-1 lists all of the assessments and indicates with an “x” when the visits are performed.

Patients must be seen for all visits on the designated day, or as close to it as possible. Missed or rescheduled visits should not lead to automatic discontinuation.

Patients, who discontinue study treatment before completing the study and will accept to remain in the study, will return for study visits as described in [Section 5.6](#). If they fail to return for these assessments for unknown reasons, every effort should be made to contact them as specified in [Section 5.6](#). At the very least, patients should be asked if they can be contacted by phone by study personnel at the date they would have been scheduled to end the follow up period (2 weeks after premature drug discontinuation) to ask about surgery and procedures, SAEs, AEs and asthma exacerbations. The following assessments are scheduled to be performed in order as follows: Patient reported outcome (PRO) questionnaires (i.e. AQLQ and ACQ), ECG, Vital signs (pulse rate, body temperature and blood pressure), blood sample/urine samples, followed by spirometry.

Table 6-1 Assessment Schedule

Period	Screening			Treatment													Post-Treatment Follow Up
	Visit Name	Screening	Run-In ^{1,2}	Treatment ³													
Days	-42 to -28	-28 to -1	1	1	42	84	112	140	168	196	224	252	280	308	336	364	378

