7. its outcome i.e., its recovery status or whether it was fatal

[figure not shown]
Conditions that were already present at the time of informed consent should be recorded in medical history of the subject.

Adverse events (including lab abnormalities that constitute AEs) should be described using a diagnosis whenever possible, rather than individual underlying signs and symptoms.

Adverse event monitoring should be continued for at least 14 days (or 5 half-lives or end of study visit, whichever is longer) following the last dose of study treatment

Information about adverse drug reactions for the investigational drug can be found in the Investigator Brochure (IB).

Abnormal laboratory values or test results constitute adverse events only if they fulfill at least one of the following criteria:

- they induce clinical signs or symptoms
 - they are considered clinically significant
 - they require therapy
- 

Clinically significant abnormal laboratory values or test results must be identified through a review of values outside of normal ranges/clinically notable ranges, significant changes from baseline or the previous visit, or values which are considered to be non-typical in subjects with the underlying disease. Alert ranges for laboratory and other test abnormalities are included in [Section 13](#).

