7.2.2 SAE reporting

To ensure patient safety, every SAE, regardless of causality, occurring after the patient has provided informed consent and until 30 days following the last administration of study treatment must be reported to Novartis safety within 24 hours of learning of its occurrence. Detailed instructions regarding the submission process and requirements are to be found in the investigator folder provided to each site.

All follow-up information for the SAE including information on complications, progression of the initial SAE and recurrent episodes must be reported as follow-up to the original episode within 24 hours of the investigator receiving the follow-up information. An SAE occurring at a different time interval or otherwise considered completely unrelated to a previously reported one must be reported separately as a new event.

If the SAE is not previously documented in the Investigator's Brochure or Package Insert (new occurrence) and is thought to be related to the study treatment, a Chief Medical Office and Patient Safety Department associate may urgently require further information from the investigator for health authority reporting. Novartis may need to issue an Investigator Notification (IN) to inform all investigators involved in any study with the same study treatment that this SAE has been reported.

Suspected Unexpected Serious Adverse Reactions (SUSARs) will be collected and reported to the competent authorities and relevant ethics committees in accordance with EU Guidance 2011/C 172/01 or as per national regulatory requirements in participating countries.

Any SAEs experienced after the 30 day period following the last administration of study treatment should only be reported to Novartis Safety if the investigator suspects a causal relationship to study treatment.

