7.6 Pregnancy reporting

To ensure subject safety, each pregnancy occurring after signing the informed consent must be reported to Novartis within 24 hours of learning of its occurrence. The pregnancy should be followed up to determine outcome, including spontaneous or voluntary termination, details of the birth, and the presence or absence of any birth defects, congenital abnormalities, or maternal and/or newborn complications.

Pregnancy should be recorded and reported by the investigator to the Novartis Chief Medical Office and Patient Safety (CMO&PS). Pregnancy follow-up should be recorded on the same form and should include an assessment of the possible relationship to the study treatment any pregnancy outcome. Any SAE experienced during pregnancy must be reported.

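### Criterion 6 ends the written contraception requirement at the last dose, while the protocol's one-week washout period covers only women stopped for contraceptive non-compliance

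*Protocol*

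**What the plan says.** Protocol section 4.2, criterion 6, excludes women of child-bearing potential "unless they are using basic methods of contraception during dosing of investigational drug". The key exclusion criteria in the protocol summary carry the same limit. The criterion then lists acceptable methods: abstinence, female sterilization, male sterilization, barrier methods, and hormonal or intrauterine methods, the last group including the pill, vaginal ring and patch.

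A post-dose period appears once. Section 5.6.2 lists the reasons for stopping study treatment. In the bullet for women who do not comply with their chosen contraception, the investigator must advise on the "continued use of effective contraception for at least one week (at least 5 half-lives of QAW039) after study drug discontinuation" and follow the woman at least to the end of that period.

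Section 10.2 describes the risks to a fetus as unknown and binds women to the contraception requirements, but gives no duration. Section 6.5.7 interrupts study drug at once after a positive urine test. The SAP does not mention contraception.

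**The concern.** The protocol names a washout interval for contraception but attaches it to one reason for stopping. How long the drug stays in the body after the last tablet does not depend on why the tablets stopped. Because the protocol calls the fetal risks unknown and stops drug immediately on a positive test, it clearly means to avoid fetal exposure. A requirement that ends on the day of the last dose does not fit that aim, and it is shorter than the interval the protocol itself considers suitable.

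What is at stake is participant safety in the week or so after dosing. Error control, power and the efficacy analysis are not affected.

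**Working it through.** No figure in the plan needs to be reproduced. The check is to compare what the protocol requires after the last dose, by reason for stopping.

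| Reason dosing ends | Post-dose contraception in the protocol text | Source |
|---|---|---|
| Contraceptive non-compliance | At least one week (at least five half-lives), as investigator advice with follow-up | 5.6.2 |
| Completion of 52 weeks | None stated | 4.2 criterion 6; 5.6.1 |
| Any other treatment discontinuation (for example a liver test abnormality or unblinding), pregnancy itself aside | None stated | 4.2 criterion 6; other bullets of 5.6.2 |
| Termination by the sponsor | None stated | 4.2 criterion 6; 5.6.5 |

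Next, whether another section closes the gap:

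- Section 5.6.1: "For all patients a safety follow-up visit should be conducted (e.g. by telephone) 14 days after last dose of study drug". It lists adverse events and SAEs as the information to collect and does not mention contraception. Day 14 also falls after a seven-day washout has passed.
- Section 5.6.5: on sponsor termination "subjects must be seen as soon as possible". This visit could carry the advice, but the text does not ask for it.
- Section 7.1 continues adverse event monitoring for 14 days or more, and section 7.2.2 requires SAE reports "until 30 days following the last administration of study treatment". Both apply to every patient, and both record events rather than prevent conception.
- Section 7.6: "each pregnancy occurring after signing the informed consent must be reported". This is reporting after the fact.
- Table 6-1 schedules a urine pregnancy test at week 52 or treatment discontinuation. It cannot inform on conception in the following week. Under section 6.5.7 there is no test at telephone contacts, apart from home tests where local rules require monthly testing.
- The local-regulation clause in criterion 6 concerns methods, not duration.

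None of these extends the requirement.

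Size of the gap: the protocol's interval is at least 7 days after the last dose and criterion 6 covers 0 days, so the shortfall is 7 − 0 = 7 days per woman at minimum.

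Who is affected: women on methods that can be stopped at once, namely barrier, pill, ring or patch. The rule that pill use be stable for three months before study drug governs starting, not stopping. Sterilization, implants and intrauterine devices do not end with dosing. Abstinence is accepted only "when this is in line with the preferred and usual lifestyle of the subject", so it is not tied to dosing either.

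**The case against.** Four points on the other side deserve weight.

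**Placement in 5.6.2.** The advice has a rationale there. Women stopped for contraceptive non-compliance are the ones already known to be poorly protected, so explicit advice and follow-up are most needed for them. That explains why the bullet contains the week. It does not explain why other women have no stated period, since their washout is the same.

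**Requirement versus protection.** A reader might infer that women lose protection at the last dose. The documents do not support that. Criterion 6 is an eligibility rule that sets a minimum, and nothing tells a woman to stop contraception with the last tablet. What ends is a written requirement.

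**Unseen sources.** Whether a post-dose period is needed depends on half-life and reproductive toxicology, which the documents do not give; the protocol refers to the Investigator's Brochure for risks. The consent form is a separate document and may already state a period. The point is therefore confined to the protocol text.

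**Quantification.** A reader might take the parenthesis in 5.6.2 to mean that one week covers five half-lives, giving a half-life of at most 168 h / 5 = 33.6 h, and from that work out how much drug remains each day. The words can equally be read as two separate minimums, and then no ceiling follows. Drug remaining is also not fetal risk. Likewise, a reader might infer that barrier users are the main group affected, but the pill, ring and patch can stop just as readily, and the documents give no method mix.

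Finally, SAP section 4 records that the sponsor terminated the study early. An amendment cannot help women already off drug.

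**Conclusion.** The point stands as a minor inconsistency in the protocol text. The protocol states a post-dose contraception interval and applies it to only one group of women, while the eligibility rule for all women ends at the last dose. The shortfall is at least one week per woman. The number of women cannot be estimated, because the documents give neither the proportion of child-bearing potential nor the methods used.

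The conclusion assumes only that washout is the same whatever the reason for stopping. It does not rest on a half-life value or on any evidence of reproductive harm; the documents contain neither. Confidence is high about what the protocol says and lower about whether women would be unprotected in practice, which depends on the unseen consent form and on what sites actually advise.

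**What to change.** Amend criterion 6, in section 4.2 and in the summary, so that contraception is required throughout dosing and for at least one week (at least five half-lives of QAW039) after the last dose. State that this applies to every woman of child-bearing potential, whatever the reason dosing ends. Align the consent form if it says something different. The follow-up duty in 5.6.2 for non-compliant women can stay as it is.

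The cost is a wording change in two places, a consent update only if needed, and about one extra week of contraception per woman. No visit, test or sample is added. Since this study has been terminated, the practical value lies in any further use of this protocol wording.

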5.1 Study treatment

5.1.1 Investigational and control drugs

The following investigational treatment will be supplied by Novartis to the study sites:

- Name: QAW039
- Formulation: tablet
- Unit dose: 2 strengths: 150 mg and 450 mg
- Name: placebos to QAW039 150 mg and QAW039 450 mg
- Formulation: tablet
- Unit dose: matching placebo to QAW039 150 mg, matching placebo to QAW039 450 mg

Please refer to the Investigator Brochure for composition of the QAW039 and placebo tablets.

The investigational treatment (tablets) will be supplied in bottles. The matching placebos for QAW039 will be identical in appearance to their active counterparts and will be identically packaged.

5.1.2 Additional treatment

On the start of the run-in period all patients will be given standard of care treatment (SoC) to be taken daily for the duration of the study:

- Open label salmeterol /fluticasone 50/500 µg b.i.d. (Seretide[®] delivered as powder via Diskus[®]/Accuhaler[®])

All patients will be provided with prednisone/prednisolone (or equivalent) tablets as the OCS for use during the study. Prednisone/prednisolone (or equivalent) will either be supplied to the investigator sites locally by Novartis or be provided by the study center and reimbursed by Novartis. The study patients will have a written asthma plan, provided by the Investigator, with instructions and information on how to self-manage their asthma daily, including taking medications appropriately and information on how to recognize and handle worsening asthma, and when, how, and who to contact in an emergency. The investigator should fill in the medication and dosage the patient should be taking during self-management. Adjustments and follow-up of the asthma worsening/exacerbation event can be managed either on the phone or during an unscheduled visit. Unscheduled visits can be necessary to evaluate the best treatment escalation for the patient's current situation. This follows common medical practice, by which patients are prescribed OCS to be self-administered at home based on symptoms (Partridge 2004). The study patients will be instructed to make every effort to call the Investigator before taking the oral steroid and if not possible, as soon as they can, but not later than 48 hours after OCS intake has started.

All patients will be provided with Short-acting Beta-agonist (SABA) (salbutamol/albuterol) which they will be instructed to use throughout the study as rescue medication to treat asthma symptoms on an 'as needed basis'. SABAs will either be supplied to the investigator sites locally by Novartis or be provided by the study center and reimbursed by Novartis.

5.2 Treatment arms

Patients will be assigned at randomization visit to one of the following 3 treatment arms in a ratio of 1:1:1

- QAW039 150 mg once daily (one tablet of blinded QAW039 at 150 mg dosage strength to be given together with one tablet blinded placebo to QAW039 450 mg)
- QAW039 450 mg once daily (one tablet of blinded QAW039 at 450 mg dosage strength to be given together with one tablet blinded placebo to QAW039 150 mg)
- Placebo to QAW039 once daily (one tablet blinded placebo to QAW039 150 mg and one tablet blinded placebo to QAW039 450 mg)

Patients will be instructed to take their investigational treatment (QAW039 or placebo) once daily in the morning without regard to time of food intake. SoC asthma therapy will be taken as directed by the investigator.

5.3 Treatment assignment and randomization

At randomization visit, all eligible subjects will be randomized via Interactive Response Technology (IRT) to one of the treatment arms. The investigator or his/her delegate will contact the IRT after confirming that the patient fulfills all the inclusion/exclusion criteria. The IRT will assign a randomization number to the patient, which will be used to link the patient to a

treatment arm and will specify unique medication numbers for the first packages of study drug to be dispensed to the patient. The randomization number will not be communicated to the caller.

The randomization numbers will be generated using the following procedure to ensure the treatment assignment is unbiased and concealed from subjects and investigator staff. A patient randomization list will be produced by the IRT provider using a validated system that automates the random assignment of patient numbers to randomization numbers. These randomization numbers are linked to the different treatment arms, which in turn are linked to medication numbers. A separate medication list will be produced by or under the responsibility of Novartis Global Clinical Supplies using a validated system that automates the random assignment of medication numbers to packs containing the investigational drug(s).

Randomization will be stratified by peripheral blood eosinophil counts at Run-in Visit (< 250 cells/ml or \geq 250 cells/ml).

The randomization scheme for subjects will be reviewed and approved by a member of the Randomization Group.

